5.3. Strategies to avoid missing data and increase adherence

To reduce missing data, the pilot study has been designed to minimise the number of questions, avoiding participants feeling overwhelmed, which could lead to incomplete responses.

Within the app, certain responses will be required for participants to progress to the next steps or level up. While this approach is intended to increase engagement, some missing data may still occur. Additionally, phone call or email follow-ups have been considered for non-responders; however, challenges may persist, as this study targets a preventive population rather than patients, and might be less motivated to engage.

The pilot study will serve as a test for retention and adherence. Based on its findings, adjustments and mitigation strategies will be designed and implemented for the subsequent randomised controlled trial (RCT) to optimise participation and data completeness.

6. Study intervention(s) or experimental manipulation(s)

6.1. Control group (CG) intervention

The control intervention consists of receiving an **informative leaflet** with a **summary of the clinical recommendations for cancer prevention**.

This document already exists in the ICO cancer screening program and will be adapted to Italian and Romanian for use in IEO and UMFCD, respectively. An English version can be found in Annex 10.1. To standardise this intervention, the translated informative leaflet will be delivered to control participants at each centre in their national language after randomisation.

6.2. Experimental group (EG) intervention: iBeChange platform

Participants allocated to the experimental group will have access to the **iBeChange platform**. This stepped-care app **provides personalised recommendations to promote behavioural change** according to participants' habits and needs.

In the beginning, participants will be asked for their habits regarding Smoking, Alcohol consumption, Nutrition, and Physical activity, and also for their Emotional well-being status, including Perceived Stress, Anxiety and Depressive symptoms, Perceived Social support, and Insomnia (Step 1). This health habit assessment will be transformed into scores according to compliance with clinical guidelines for cancer prevention (Health Habit Scores [HHS]) and displayed to the user. (Figure 2).

[figure not shown]
Figure 2. Participant's health habit status visualisation in the iBeChange platform

According to the participant's health habits, emotional status, and preferences (Step 2), further questions are administered to understand the motivational status of change and the main barrier/promoters of the target behaviours. This was designed based on **behavioural change models** such as the Health Action Process Approach (HAPA)³⁰ and the Capability-Opportunity-Motivation – Behaviour (COM-B) models^{31,32} (Step 3).

Considering all previously gathered information and the participant's choice of the habit to start working on (Step 4), 12 weeks of stepped care tailored intervention will start (Step 5). It will be structured with **weekly Missions** – specific and measurable behaviours to be performed and monitored in one week. By achieving the weekly mission, the participant's habits will be closer to clinical recommendation guidelines for cancer prevention. For a personalised intervention, the iBeChange platform relies on a Recommender system based on Reinforcement learning, which will collect participant's interactions and accomplishments in the app to fine-tune which and when recommendations and resources are delivered (**Figure 3**).

Figure 3. Participant's journey in the iBeChange platform

Participant's iBeChange Journey

6.2.1. Intervention levels

The stepped care intervention will contain the following intervention levels:

- Level 0: In this intervention level, **automatic** recommendations and resources will be delivered to support the achievement of the weekly missions. Among these, the possibility to enter a group chat for social support among participants named iBeChange community can also be assigned.

Once every 4 weeks, the full health habit assessment (for more detail, refer to section 6.2. on the page before) will be administered (at baseline, 4 weeks, and 8 weeks).

In addition to the weekly mission monitoring, the emotional distress thermometer in the visual analogue scale (0-10) form will be assessed every 2 weeks. In case the answer > 5, PSS-4 and PHQ-4 will be administered to detect stress, anxiety or depression levels. If any of these are moderate or high, participants will be escalated to Level 1.

If the participant agrees to voice recording, after the emotional distress thermometer assessment, the question "How stressed do you feel right now?" will be displayed asking users to speak and record the answer.

- Level 1: In this intervention level, participants will be able to contact a **healthcare professional** via chat to solve doubts about their behavioural change strategy or emotional well-being status. This interaction will be initiated by the participant.
- Level 2: Participants in this level will receive a single-session healthcare professional intervention. This will be a one-hour online session with a motivational interview structure, in which the participant's needs and potential barriers for behavioural change will be addressed.

Techniques and interventions with effective evidence will be administered according to the participant's symptom or situation.

To standardise intervention Level 2, a detailed professional single-session protocol has been developed. After the session, professionals will register the techniques used for proper monitoring of the intervention.

- Level 3: For those participants whose healthcare needs exceed the reach of iBeChange, a referral to specialised services will be required. This is the case when severe mental health problems or psychological emergencies are suspected. Participants receiving Level 3 intervention will be categorised as high-risk users. The time points and criteria for intervention level escalation of participants are summarised in the following table for each health pillar. Criteria for escalation to Level 3 are further detailed in Annex 10.2.

The criteria for escalation to Level 1, Level 2 and Level 3 for the different health pillars is described in Table 7 below.

Table 7. Criteria for intervention escalation to Level 1, Level 2 and Level 3 in the iBeChange platform for each health pillar

Criteria for intervention escalation to:

	Level 1 Chat with professional	Level 2 Professional single- session intervention (SSI)	Level 3 Referral to specialised services	
Smoking	Weekly: If not achieving the weekly mission for 3 attempts At month 1 and at month 2: If the participant increases 2 points or more in the Smoking health habit score (HHS).	After Level 1: If not achieving the weekly mission after 3 attempts At month 2: If the participant increases 2 points or more in the Smoking health habit score (HHS).	After scheduling SSI, if participants do not attend to one SSI and do not accomplish a mission for two consecutive weeks. At SSI, if a major mental health problem that hinders smoking cessation is suspected.	
Alcohol	Weekly: If not achieving the weekly mission for 3 attempts At month 1 and at month 2: If the participant decreases 2 points or more in the Alcohol health habit score (HHS).	After Level 1: If not achieving the weekly mission after 3 weeks At month 2: If the participant decreases 2 points or more in the Alcohol consumption health habit score (HHS).	After scheduling SSI, if participants do not attend to one SSI and do not accomplish a mission for two consecutive weeks. At SSI, if a major mental health problem that might hinder alcohol consumption cessation is suspected.	

Nutrition	Weekly: If not achieving the weekly mission after 3 attempts At month 1 and at month 2: If the participant drops 2 points or more in the Nutrition health habit score (HHS).	After Level 1: If not adherent to missions for 3 weeks At month 2: If the participant drops 2 points or more in the Nutrition HHS.	If partially or non- compliant HHS and BMI <18.5 or ≥40 kg/m².
Physical activity	Weekly: If not achieving the weekly mission for 3 attempts At month 1 and at month 2: If the participant drops by 100 METs in the Physical Activity health habit score (HHS).	After Level 1: If not achieving the weekly mission after 3 weeks At month 2: If the participant drops by 100 METs or more in the Physical Activity health habit score (HHS).	After scheduling SSI, if participants do not attend to one SSI and do not accomplish a mission for two consecutive weeks. At SSI, if a major mental health problem or other potentially impairing aspect that might hinder physical activity is suspected.
Emotional Well-being	At baseline: If acting on Stress, Anxiety and Depression but still presenting symptoms Weekly: Not achieving the weekly mission	At month 1 and at month 2: If adherent to missions but shows no improvement in PSS-4 and PHQ-4.	At SSI, if a full major mental health problem is suspected, according to the developed List of Standardized criteria (Annex 10.2).

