4.4. Effectiveness data collection

Effectiveness measurement time points will be at baseline and after 12 weeks.

Among secondary outcome measures to assess the iBeChange intervention effectiveness compared to the control group (described in Table 3), one main secondary measure has been selected per health habit or psychosocial measure according to those behaviours or symptoms with most evidence of cancer risk. These are the following:

- Smoking: Number of smoked cigarettes per day
- Body Weight: Body mass index calculation
- Alcohol: Weekly alcohol consumption
- Nutrition: Intake of processed food and red meat per week
- Physical activity: Minutes of moderate to vigorous physical activity per week
- Psychosocial: PSS-4 score for perceived stress.

4.4.1. iBeChange questionnaire on Cancer Nutritional factors

After a thorough literature review, there were some extensively used nutrition questionnaires assessing for adherence to the Mediterranean diet. However, this is not the scope of this pilot study: we aim to specifically assess the nutritional groups associated with increased or decreased risk of cancer. No validated scale assessing these specific constructs was found. Therefore, the iBeChange consortium is developing an iBeChange questionnaire on Cancer Nutritional factors. Questions will be selected and validated through experts' panels in an iterative manner. A paper-

format protocol detailing the development and validation of the scale will be attached to this pilot protocol submission for IRB approval.

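### Table 7 escalates on a rise in the smoking health habit score but on a fall in the other three; if smoking is also scored higher-is-better, its trigger is reversed

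*Protocol*

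**What the plan says.** Protocol 6.2 introduces the HHS once for all pillars. The habit assessment is "transformed into scores according to compliance with clinical guidelines for cancer prevention (Health Habit Scores [HHS", and the result is shown to the user. The readable text does not say whether a high score is good or bad for any pillar.

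Protocol 6.2.1, Table 7, then uses changes in these scores as escalation rules:

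- Smoking, Level 1 at months 1 and 2, and Level 2 at month 2: "If the participant increases 2 points or more in the Smoking health habit score (HHS".
- Alcohol, Level 1 at months 1 and 2: "If the participant decreases 2 points or more in the Alcohol health habit score (HHS".
- Alcohol, Level 2 at month 2: "If the participant decreases 2 points or more in the Alcohol consumption health habit score (HHS".
- Nutrition, Level 1 at months 1 and 2: "If the participant drops 2 points or more in the Nutrition health habit score (HHS", with the same direction at Level 2.
- Physical activity, Level 1 at months 1 and 2: "If the participant drops by 100 METs in the Physical Activity health habit score (HHS", with the same direction at Level 2.

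The emotional well-being row uses PSS-4 and PHQ-4 rather than an HHS. Section 6.2.1 schedules the full habit assessment at baseline, 4 weeks and 8 weeks. Level 1 opens a chat that the participant has to start. Level 2 is a one-hour online session with a professional.

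**The concern.** Smoking and alcohol are both habits where less is better, and both scores are introduced as compliance scores, yet their triggers point in opposite directions. Smoking is the only one of the four score-based rows that triggers on a rise. Section 3.1 reserves professional support for people who have not adhered or responded to the automated level, so every score trigger should catch worsening. A row with the wrong sign would do the opposite: spend sessions on people who improved and pass over those who got worse. These are working rules for the app, fixed in the protocol, and not a detail that an analysis plan would supply. The last scheduled score is at week 8, so no later score check would correct a wrong call.

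**Working it through.** No figure in the plan needs reproducing. The check is whether each row catches worsening under each possible scoring direction.

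**Score occasions.** The score-based pillars are smoking, alcohol, nutrition and physical activity, which makes 4. Each has a score check at month 1 and at month 2. That gives 4 × 2 = 8 occasions. At month 2 the same score feeds both the Level 1 and the Level 2 cell, so it is counted once.

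**Assumption.** Nutrition and physical activity are taken as higher-is-better, since both trigger on a drop.

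| Smoking score | Alcohol score | Smoking row | Alcohol row | Reversed occasions |
|---|---|---|---|---|
| higher is better | higher is better | reversed | right | 2 of 8 |
| higher is worse | higher is worse | right | reversed | 2 of 8 |
| higher is worse | higher is better | right | right | 0 of 8 |
| higher is better | higher is worse | reversed | reversed | 2 + 2 = 4 of 8 |

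**Which case fits the text.** Scores based on compliance most naturally rise with compliance, and three of the four rows follow that pattern. This is the first line of the table: the smoking row is the one reversed. A smoker whose score rises by 2 points at month 2 has then improved, yet meets the criterion for both the chat and the session. A smoker whose score falls by 2 points has worsened and meets neither score criterion.

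**What still catches a worsening smoker.** There are two other routes:

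- Three failed attempts at the weekly mission lead to Level 1, and continued failure after Level 1 leads to Level 2. Section 6.2 lets participants choose the habit they start on, so someone working on another habit may have no smoking mission to fail. That is an inference from the text.
- The two-weekly distress thermometer can lead, through PSS-4 and PHQ-4, to Level 1. It is not specific to smoking.

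**People affected.** The number cannot be computed, because the document gives neither the score ranges nor the share of smokers. The upper limit is the 90 participants planned for the experimental group (section 8.2). Within it, only smokers whose score moves by 2 points or more are affected.

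**The case against.** The strongest reply is that no error has been shown. Compliance scores need not share a scale or a direction. The physical activity score is expressed in METs, the nutrition score also has compliance categories, and the emotional row uses other instruments, so pillar-specific scoring is plausible. The smoking and alcohol rows each keep the same direction at Level 1 and Level 2, which fits a deliberate row-specific rule as well as it fits a slip. Figure 2, which displays the scores, was lost when the text was extracted. Section 7.2.2 also refers to an app specification diagram that is not at hand. Either could state the direction, and their absence here does not count against the plan.

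This stands as far as certainty goes. A reader might infer that the smoking row is definitely wrong; the documents do not support that, because the third line of the table above remains possible. A reader might also infer that the alcohol row is just as suspect, because section 4.4 names consumption measures as the main outcomes ("Smoking: Number of smoked cigarettes per day" and "Alcohol: Weekly alcohol consumption"). That argument is weak. Those are trial outcomes, not the HHS, and section 8.7 shows that the app can use a different instrument from the outcome set (IPAQ beside GPAQ).

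It is also fair to say that the intent is clear and the harm bounded. A wrong Level 1 call only opens a chat, and failed missions still escalate. What the reply does not remove is that the rule as written, read with the compliance definition in 6.2, can misfire for smokers.

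**Conclusion.** The point holds in conditional form and is minor. Table 7 gives smoking the opposite trigger direction from the other three score-based rows, while 6.2 introduces all the scores together as compliance scores. If smoking follows that definition with higher as better, its score trigger is reversed at both months, which is 2 of 8 score occasions. The smoking and alcohol rows are both right only under opposite scoring, with smoking higher-is-worse and alcohol higher-is-better, which the readable text does not state.

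Two further readings go too far. Worsening smokers would not be left without any route to support, since the mission and distress routes remain, though they are partial. The trial's inference is not undermined either: no hypothesis and no sample size figure depends on the trigger. The cost would be misdirected professional time and missed support for some smokers in the experimental group.

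**What to change.** Before the pilot starts:

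1. Reword every score trigger in Table 7 as *worsens by 2 points or more* (*worsens by 100 METs or more* for physical activity). This is right under any scoring direction.
2. Confirm the direction of each pillar's HHS and state it in section 6.2.
3. Check that the app's escalation logic matches.

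Do not simply change the smoking row to a decrease: if that score runs higher-is-worse, the change would create the error it is meant to remove.

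The cost is a sentence per pillar, a wording change in up to 8 table cells (4 pillars × 2 levels), and one check of the app logic. No design parameter or analysis changes.

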5.1. Inclusion and Exclusion criteria

Table 4. Inclusion and Exclusion criteria for the iBeChange Pilot Study

	✓ IC1. Ability to understand and voluntarily provide signed written informed consent approved by the study site's Institutional Review Board (IRB).
Inclusion criteria	✓ IC2. Being at a high-risk age for breast (women between 45-70), colorectal (individuals between 50-70) or lung cancer (individuals aged 50-80 years).
	✓ IC3. Having participated in a test for early detection of cancer (i.e., mammography or ultrasound for breast cancer, faecal occult blood test (FOBT) or colonoscopy for colorectal cancer, and CT-scan for lung cancer).
	- EC1. History of any prior or current personal cancer diagnosis. In the case of colorectal and breast cancer, this will be restricted to the pathology tested for screening.
Exclusion criteria	- EC2. Current severe disease that may significantly compromise the performance on the study according to the criteria of the investigator.
	- EC3. Not owning a smartphone.
	 EC4. For breast and colorectal cancer, participants undergoing screening for alert symptoms or family history of these cancer types (the latest are eligible for specific hereditary cancer programs).

Regarding EC2, the term "severe disease" is broadly defined to include conditions that would prevent participants from fully engaging in the study's activities. The criteria remain intentionally broad to allow flexibility in assessing potential participants. Specific examples may be refined as cases arise during the pilot study. Examples of excluded conditions:

Physical disabilities such as blindness or deafness, particularly in cases where the technology (e.g., mobile applications) is not adapted for these impairments, are examples of conditions that would prevent participation.

Participants with severe mental illness or cognitive impairments that hinder their ability to understand and navigate the app will be excluded from the study. Severe mental illness will not automatically lead to exclusion; instead, such cases will be referred to general practitioners for appropriate care.

As for EC3, there is no feasible solution for providing smartphones to those without them due to logistical and financial constraints. Past studies attempted to loan devices, but it was not possible in this case.

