10.2. List of Standardized Criteria for Level 3 intervention escalation

If any of the items listed below are suspected in a participant during the professional SSI, they will be referred to external professional assistance but keep the iBeChange support in parallel:

- Depressed mood most of the day, for at least 2 consecutive weeks, represents a difference from previous functioning.
- Important decrease in interest or pleasure in almost all activities most of the day, for at least 2 consecutive weeks, representing a difference from previous functioning.

NOTE: Ensure these two risk factors are not due to a recent bereavement process.

- Excessive worry about various events presents more than half the time for approximately 6 months.
- Other anxiety symptoms include: feeling restless, tense, panic, experiencing periods of
 increased heart rate, hyperventilation, sweating, trembling, or having trouble
 concentrating. These symptoms significantly interfere with the person's daily
 functionality.
- Indicators of Post-Traumatic Stress Disorder: 1) memories, nightmares, flashbacks; 2) persistent avoidance; 3) intense physiological reactions of hyper-arousal or other behaviours as if the traumatic event were occurring. These symptoms cause significant emotional distress and last more than 1 month.
- Risk behaviours or self-harm (including substance abuse and eating disorders).
- Recurrent thoughts of death or suicide.
- Significant cognitive impairment.
- Active psychotic symptomatology: disorientation (in time, place, or person), severely disorganised thinking and/or behaviour, hallucinations, and delusional ideas.
- Being a victim of psychological or physical abuse.
- Any other psychological symptom that generates significant functional impairment in any area of their life.

11. Conclusions

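### In Table 7's Emotional Well-being row, a non-adherent participant whose distress scores stay moderate or high is held at a chat that the participant must start

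*Protocol*

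**What the plan says.** All of this is in the Protocol, section 6.2.1 and Table 7, with Level 3 detailed in Annex 10.2.

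- **Level 1, Emotional Well-being row:** "At baseline: If acting on Stress, Anxiety and Depression but still presenting symptoms Weekly: Not achieving the weekly mission". The text above the table adds that a distress thermometer score above 5, asked every two weeks, prompts the PSS-4 and PHQ-4. A moderate or high result on these moves the participant to Level 1.
- **What Level 1 is:** a chat with a healthcare professional. "This interaction will be initiated by the participant".
- **Level 2 (the single-session intervention, SSI), same row:** "At month 1 and at month 2: If adherent to missions but shows no improvement in PSS-4 and PHQ-4".
- **Level 3 (referral), same row:** "At SSI, if a full major mental health problem is suspected, according to the developed List of Standardized criteria (Annex 10.2"). Annex 10.2 opens in the same way: "If any of the items listed below are suspected in a participant during the professional SSI, they will be referred to external professional assistance".
- **Other pillars:** the Nutrition row's Level 2 cell reads "After Level 1: If not adherent to missions for 3 weeks", and Smoking, Alcohol and Physical activity have equivalent clauses. Those three rows also refer to Level 3 "After scheduling SSI, if participants do not attend to one SSI and do not accomplish a mission for two consecutive weeks".

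**The concern.** In this row, being adherent is a condition for receiving more help. Someone who disengages from the missions while remaining distressed fails that condition, although this combination is a good reason for a professional to make contact. The scores that would show the problem are collected by the app, yet in this row they lead no further than a chat that the participant has to open.

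Annex 10.2 lists suicidal thoughts, self-harm and psychotic symptoms among its reasons for referral, but looks for them during the session. Section 5.1 says "Severe mental illness will not automatically lead to exclusion", so such problems may be present or may emerge during the 12 weeks. Section 3.1 also describes the stepped structure as freeing professionals for people who did not adhere or respond. Requiring adherence for the session fits poorly with that aim, and the Protocol gives no reason for treating this pillar differently.

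**Working it through.** The Protocol states no figure here, so the check is a trace through its rules.

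**1. Trace one participant through the row.** Take a participant in the Emotional Well-being pillar who is not adherent and whose PSS-4 or PHQ-4 stays moderate or high.

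| Event | Rule | Result |
|---|---|---|
| Weekly mission missed | Table 7, Level 1 cell | Level 1 |
| Thermometer above 5, then moderate or high PSS-4 or PHQ-4 | Section 6.2.1, Level 0 text | Level 1 |
| Month 1 and month 2 review | Table 7, Level 2 cell requires adherence | Condition fails, stays at Level 1 |
| Referral | Table 7, Level 3 cell and Annex 10.2 operate at the SSI | Not reached through this row |

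Over 12 weeks the thermometer is asked about 12 / 2 = 6 times, and the full assessment is repeated at weeks 4 and 8. Under this row, none of these occasions moves the participant beyond Level 1.

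**2. Compare the five rows.**

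- Continued missed missions or non-adherence after Level 1 lead to Level 2 in Smoking, Alcohol, Nutrition and Physical activity: 4 of 5 rows. Emotional Well-being is the exception.
- Non-attendance at the SSI combined with missed missions leads to Level 3 in Smoking, Alcohol and Physical activity: 3 of 5 rows. Emotional Well-being has no such clause.

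**3. Timeline if every mission is missed, assuming one attempt per week.** In the other four rows, Level 1 comes at week 3 and Level 2 at week 3 + 3 = 6. In the Emotional Well-being row, Level 1 opens at week 1, and Level 2 is not reached through that row in the 12 weeks.

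**4. Look for routes outside the row.**

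- The general description of Level 3 in section 6.2.1 calls for referral when severe mental health problems or emergencies are suspected, and it names no session. It then hands the criteria to Table 7 and Annex 10.2. For someone at Level 1, a professional's suspicion would in practice have to arise in a chat, which the participant must start.
- A participant may reach an SSI through another pillar's row, by missed missions there or by a worse health habit score at month 2. Annex 10.2 would then apply. That route depends on the other behaviour and not on PSS-4 or PHQ-4.

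Neither route gives staff-initiated contact because of the distress scores.

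**The case against.** The strongest reply is that the safety net is wider than this one row. A reader might infer from Table 7 that such a participant can never be referred. The Protocol does not support that: the general Level 3 sentence is not tied to the session, and other pillars' rows can lead to one. This stands, and it limits the point to one row and to contact driven by the distress scores.

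Three further replies carry some weight.

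- Level 1 is itself access to a professional, and this row opens it at the first missed mission, where the others wait for three attempts. That is true, but access is not contact when the participant has to begin it.
- The term *adherent* is not defined, and the row uses different words for adhering to missions and achieving them. Someone who tries and fails may count as adherent and so qualify. The affected group may therefore be smaller than it first appears, but those who stop attempting missions remain in it.
- Section 5.1 does exclude severe mental illness that prevents a person from understanding or using the app, and section 3.2.1 describes the study as minimal risk. This lowers the expected number of serious cases. It does not deal with distress that emerges later.

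A reader might also infer that an adherent participant with stable low scores is sent to the session, because the Level 2 cell names no symptom level. That depends on reading the cell apart from the stepped sequence. If levels are taken in order, such a participant may never enter Level 1. The Protocol does not settle this, so the point is not made here.

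Section 6.2.1 mentions a separate protocol for the session. It is described as standardising the session's content, not as deciding who receives one.

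**Conclusion.** The point holds within the Emotional Well-being row. A non-adherent participant with persistent moderate or high PSS-4 or PHQ-4 stays at a participant-initiated chat, and the row's referral trigger lies beyond a session for which that participant does not qualify. The general referral sentence and the other rows narrow this gap without closing it.

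This is a cheap improvement for participant safety. It has no claimed effect on a feasibility threshold or on any planning figure for the full RCT. How many people it concerns cannot be derived from the Protocol. Purely for scale, if 1% to 10% of the 90 in the experimental group were affected (an assumption), that would be 90 × 0.01 = 0.9 to 90 × 0.10 = 9 people.

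The conclusion rests on taking Table 7 and Annex 10.2 as the operative criteria, as section 6.2.1 says they are, and on a reading of *adherent* that leaves out people who have stopped doing missions.

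**What to change.** 1. **Level 2 cell.** Replace it with: *at month 1 and at month 2, if PSS-4 or PHQ-4 is moderate or high and that scale has not improved since baseline, whether or not missions were achieved*.
2. **Between reviews.** Allow the same step when a two-weekly thermometer follow-up again gives a moderate or high PSS-4 or PHQ-4 after Level 1.
3. **Level 3 cell and Annex 10.2.** State that the listed criteria also apply when suspected in the Level 1 chat, not only at the SSI.
4. **Clauses borrowed from other rows.** If a missed-mission trigger or the SSI non-attendance clause is added to this row, apply it only when the last PSS-4 or PHQ-4 was moderate or high. Without that condition, a low-scoring participant who simply stops using the app could be sent to a session, or to specialist referral and the high-risk category.

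The cost is two table cells, one sentence in the Annex and the matching app rules. There would also be some extra one-hour online sessions by professionals already in the plan; the number is probably small but is not derivable from the Protocol. Under item 1, any adherent, unimproved participant below the cut-off whom the present cell admits would no longer qualify. If the clinical leads want to keep that group, the present cell can stay as a second, alternative trigger.
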